6.3 Other Sets Defined for Tables and Listings

For the purposes of tables and listings the following set is defined:

- Enrolled Set: all subjects who provided informed consent for the study.

7 General Considerations for Statistical Analysis

7.1 Statistical Significance

There is no hypothesis testing or confidence interval (CI) calculation performed hence statistical significance is not applicable.

7.2 Multiplicity

Since there is no hypothesis testing involved, multiplicity adjustment is not applicable.

7.3 Handling of Missing Data

The number of subjects with missing data will be presented under a “Missing” category. Unless otherwise stated, missing values will not be included in the denominator count when calculating percentages.

When quantitative variables are being summarised, only the non-missing values will be evaluated for calculating summary statistics.

7.3.1 Missing/Incomplete Dates:

Medications:

In case of missing or incomplete dates not directly allowing allocation to any category of medications, a worst-case allocation will be done according to the available parts of the start and the stop dates. The medications will be allocated to the first category allowed by the available data, according to the following order:

- Concomitant medication;
- Post-Study medication;
- Prior medication.

Procedures:

In case of missing or incomplete dates not directly allowing allocation to any category of procedure, a worst-case allocation will be done according to the available parts of the start and the stop dates. The procedure will be allocated to the first category allowed by the available data, according to the following order:

- Concomitant procedure;
- Post-Study procedure
- Prior procedure.

Adverse events:

In case of missing or incomplete date/time not directly allowing allocation to any of the category of AEs, a worst-case allocation will be done according to the available parts of the start and the stop dates/times. The AE will be allocated to the first category allowed by the available data, according to the following order:

- Treatment emergent;
- Post-study;
- Pre-treatment.

Missing severity of adverse events:

In case of missing severity, the severity will not be imputed and will be reported as “Missing”.

Other critical missing data, if any, will be discussed during the review of the data. Decisions will be fully documented in the DRR.

7.4 Covariates

Not applicable.

7.5 Interim Analyses

No interim analysis will be performed.

7.6 Examinations of Subgroups

No subgroup analysis will be performed.

7.7 Descriptive Statistics

PK variables (except for t_{max} , t_{max_inh} and t_{max_iv}) will be summarized by means of descriptive statistics including n (number of observed values), arithmetic mean, standard deviation (SD), coefficient of variation (CV), geometric mean, geometric CV, median, minimum and maximum. t_{max} , t_{max_inh} , t_{max_iv} will be summarized by using n, median, minimum and maximum.

Descriptive statistics for quantitative variables will include n (the number of non-missing values), mean, standard deviation (SD), median, minimum and maximum values.

Categorical variables will be summarised by using frequency count and percent distributions.

7.8 Definitions

7.8.1 Baseline and Change from Baseline

Baseline values are defined as the last evaluation before the first treatment dose (Inhalation).

For each of the above variable, change from baseline is defined at each post-dose as:

Post-dose value – baseline value.

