#### Vital signs

Percentage of subjects with clinical relevant changes from baseline to 2,5 hrs post-dose in SBP and DBP defined as

- Change from pre-dose in DBP > 10 mmHg;
- Change from pre-dose in SBP > 20 mmHg;

will be summarized.

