10.3 Vital Signs

For the purpose of safety analyses, the mean of triplicate measurements of systolic blood pressure (SBP) and diastolic blood pressure (DBP) will be used. The mean SBP and DBP values at baseline and at 2.5 hours post- dose will be summarized using descriptive statistics. Change from baseline to 2.5 hours post-dose in mean SBP and DBP will also be summarized.

Number and percentage of subjects with clinically relevant changes from baseline to 2.5 hours post-dose in SBP and DBP will be summarized. Clinically relevant changes are defined as:

- Change from baseline in SBP > 10 mmHg
- Change from baseline in DBP > 20 mmHg

10.4 12-lead Safety Electrocardiogram

Triplicate ECG measurements will be averaged on available values and the average value will be used to calculate summary statistics for heart rate (HR), PR interval (PR), QRS interval (QRS) and QTcF interval (QTcF)..

Baseline value (i.e. pre dose value) and 2.5 hours post dose will be summarized.

Number and percentage of subjects with clinically relevant change in HR at 2.5 hours post-dose defined as change from baseline > 20 bpm, will also be summarized.

The number and the percentage of subjects with QTcF abnormalities defined as:

- QTcF >450 ms,
- QTcF >480 ms
- QTcF >500 ms;
- change from baseline to 2.5 Hours post dose in QTcF >30 ms
- change from baseline to 2.5 Hours post dose in QTcF >60 ms;

will be summarized.

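### The counts of clinically relevant change in SBP, DBP and HR can only capture increases, although neither document limits them to increases

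*SAP*

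**What the plan says.** SAP 7.8.1 sets the reference point: "Baseline values are defined as the last evaluation before the first treatment dose (Inhalation"). It then states that "change from baseline is defined at each post-dose as" follows: "Post-dose value – baseline value", which is a signed difference.

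SAP 10.3 plans this output for blood pressure: "Number and percentage of subjects with clinically relevant changes from baseline to 2.5 hours post-dose in SBP and DBP will be summarized". Its two criteria are "Change from baseline in SBP > 10 mmHg" and "Change from baseline in DBP > 20 mmHg". SAP 10.4 uses the same form for heart rate: "clinically relevant change in HR at 2.5 hours post-dose defined as change from baseline > 20 bpm". None of the three uses an absolute value, mentions decreases or gives a negative limit.

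Protocol 12.3.5 introduces its blood pressure criteria with "Percentage of subjects with clinical relevant changes from baseline to 2,5 hrs post-dose in SBP and DBP defined as". It lists DBP above 10 mmHg and SBP above 20 mmHg, and in the ECG part HR above 20 bpm. It names no direction either. Its blood pressure limits are the reverse of those in the SAP, while SAP section 12 states that the protocol-defined analysis is unchanged.

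**The concern.** A rule labelled as counting relevant changes would normally be read as covering movement both ways. Combining a signed difference with a positive limit makes it one-sided without saying so. A reader of the final table could take a low percentage to mean that blood pressure and heart rate were stable, when the table speaks only to rises.

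Safety and tolerability is a stated objective. Protocol 1.3 notes that the compound has not been given intravenously to humans before. The safety plan has one post-dose reading of blood pressure and ECG heart rate, at 2.5 h after inhalation, that is, half an hour after the infusion ends. The eligibility criteria in Protocol 4.2 set lower as well as upper bounds (SBP 90-140 mmHg, DBP 40-90 mmHg, HR 40-110 bpm), so low values matter elsewhere in the same protocol.

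**Working it through.** The documents give no flag rate, power figure or standard deviation for these measures, so there is no planned figure to reproduce. The check is of the rule itself.

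**Inputs.** Change D = post-dose minus baseline (SAP 7.8.1). SAP limits: SBP 10, DBP 20, HR 20 (SAP 10.3 and 10.4). Protocol limits: SBP 20, DBP 10, HR 20 (Protocol 12.3.5). Upper eligibility bounds: SBP 140, DBP 90, HR 110 (Protocol 4.2). Planned subjects: 8 (SAP section 5).

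**Step 1: the rule as written.** A subject is counted if D > L, with L positive. Any fall has D < 0 < L and so is never counted. Example: SBP from 130 to 90 gives D = 90 - 130 = -40, which exceeds neither 10 nor 20.

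**Step 2: every whole-number fall from 1 up to the upper eligibility bound.** This range is exhaustive by design and is not meant to be realistic. The rule as written is compared with one using the size of the change, |D| > L.

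| Measure | Falls tested | Counted, D > L (either document's limits) | Counted, \|D\| > L, SAP limits | Counted, \|D\| > L, protocol limits |
|---|---|---|---|---|
| SBP | 140 | 0 | 140 - 10 = 130 | 140 - 20 = 120 |
| DBP | 90 | 0 | 90 - 20 = 70 | 90 - 10 = 80 |
| HR | 110 | 0 | 110 - 20 = 90 | 110 - 20 = 90 |

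The one-sidedness does not depend on which document's limits are used.

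**Step 3: weight of one subject.** 1/8 = 12.5 percentage points.

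**Step 4: illustration only.** Assume D is normal with mean zero and an SD between 5 and 15; the documents give no SD. Then P(D > L) = 1 - Φ(L/SD), and the two-sided probability is twice that.

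| Limit | SD | D > L | \|D\| > L | Expected count of 8 |
|---|---|---|---|---|
| 10 | 5 | 2.3% | 4.6% | 0.18 vs 0.36 |
| 10 | 10 | 15.9% | 31.7% | 1.27 vs 2.54 |
| 10 | 15 | 25.2% | 50.5% | 2.02 vs 4.04 |
| 20 | 10 | 2.3% | 4.6% | 0.18 vs 0.36 |
| 20 | 15 | 9.1% | 18.2% | 0.73 vs 1.46 |

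At limit 20 and SD 5 both probabilities are negligible. The doubling follows from the assumed symmetry and is not evidence about this compound.

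**Step 5: where else a fall would show.**
- Blood pressure: SAP 10.3 also summarises the change in SBP and DBP, and SAP 7.7 includes the minimum. If that minimum is negative, it is the largest fall in the study.
- Heart rate: SAP 10.4 summarises the baseline and 2.5 h values. It plans no summary of the change other than the flag. Two separate minima do not give the largest within-subject fall.
- All measures: SAP 7.10 lists all eCRF data, and SAP 13.2.2 gives decimal rules for listed changes from baseline.
- Adverse events: Protocol 10.8 requires changes the investigator considers clinically significant to be reported as adverse events.

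None of these gives the number of subjects whose fall passed a limit.

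**Step 6: the swapped limits.** Take a rise of 15 mmHg. In SBP it is counted under the SAP (15 > 10) but not under the protocol (15 < 20). In DBP it is counted under the protocol (15 > 10) but not under the SAP (15 < 20). The limits must be settled before any row, for rises or falls, has a fixed meaning.

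**The case against.** The best reply is that falls are already visible. The signed blood pressure change is summarised with its minimum, 8 subjects with one post-dose reading can be checked by eye in a listing, and a fall of clinical concern should appear as an adverse event. This stands. A reader might infer that marked falls would vanish from the safety reporting; the documents do not support that. The gap is confined to the counts and, for heart rate, to the missing summary of change.

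It can also be said that the protocol uses the same form of criterion and that the SAP's QTcF change flags are one-sided too. This also stands. A reader might infer that the SAP narrowed a rule meant to be two-sided, but the protocol leaves direction open and nothing shows which was intended. Nor is the signed definition itself an error: it is what lets the descriptive minimum show a fall. And no category of no relevant change is defined, so the plan does not formally classify a fall as irrelevant; it simply does not count it.

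Finally, the stakes are modest. Protocol 6.2.1 puts the intravenous dose at 18.5 µg, under 0.6% of the inhaled dose, and Protocol 1.1 reports no cardiovascular signal in earlier healthy-volunteer trials. The study is exploratory, without hypothesis tests.

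What survives is narrow. A minimum shows one extreme, not how many subjects passed a limit, and adverse event reporting rests on judgement, not a prespecified cut-off. SAP 7.8.1 also refers to variables listed above it when none are, although SAP 10.3 and 10.4 use the term and no other definition exists.

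**Conclusion.** The point holds as an incomplete count, and it is minor. As written, the flags for SBP, DBP and HR can count increases only, under either document's limits. This follows from the definitions and needs no distributional assumption. The 12.5 percentage points is the weight of any one of 8 subjects, not an estimate of bias; how many subjects would be affected cannot be derived from the documents. It rests on applying the SAP 7.8.1 definition to SAP 10.3 and 10.4, the only definition available. No bioavailability, mass balance or metabolite result is affected.

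**What to change.** 1. Reconcile the SBP and DBP limits between Protocol 12.3.5 and SAP 10.3, and correct the statement in SAP section 12 if a change is intended. Which limits apply is for the sponsor to decide.
2. In SAP 10.3 and 10.4, state the direction and report the number and percentage of subjects separately for increases and for decreases beyond the reconciled SBP and DBP limits and the HR limit. Keep the signed definition of change.
3. Add a descriptive summary of HR change from baseline to 2.5 h, as already planned for blood pressure.
4. In SAP 7.8.1, name the variables to which the definition applies.

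The cost is three extra rows, one extra summary and a short text edit. No new data are needed.

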7.8.2 Study Day

The study day relative to the date of study medication intake will be calculated as:

- date of event – date of first study drug inhalation + 1 (if date of event \geq date of first study drug inhalation);

or

- date of event – date of first study drug inhalation (if date of event $<$ date of first study drug inhalation).

7.9 Exclusion of Data from the Statistical Analyses

7.9.1 Exclusion of Data from All Statistical Analyses

There will not be any exclusions of the collected data from the statistical analyses.

7.9.2 Exclusion of Data from PK Analyses

Subjects may be excluded from the PK population and hence from the PK analysis if they fall in the cases as defined in the European Medicines Agency (EMA) "Guideline on the Investigation of Bioequivalence".

All data will be reviewed during the DRM in order to make decisions of exclusion from PK analyses and documented in the DRR.

If any data or subject is excluded from the tables or figures, a footnote will be added to notify the exclusions.

7.10 Listings

All data collected in the eCRF will be presented in the listings.

7.11 Coding

Medical and surgical history, concomitant diseases, procedures and adverse events will be coded according to Medical Dictionary for Regulatory Activities (MedDRA) version 24.0

Medications will be coded using the World Health Organization Drug Dictionary (WHO-DD) WHO Global B3 format Version -March 2021.

8 Study Population

8.1 Disposition of Subjects and Discontinuations

8.1.1 Disposition of Subjects

The number of subjects treated, who completed treatment period and who completed the follow-up will be summarized. All subjects will be included.

8.1.2 Discontinuation from the Study

The number and percentage of subjects who completed the study, withdrew from the study and the number and percentage of subjects with each reason for withdrawal from the study and from the treatment period will be presented on Enrolled Set.

8.1.3 Protocol Deviations and Analysis Sets

Deviations will be classified according to the following categories:

- Violation of Inclusion Criterion;
- Violation of Exclusion Criterion;
- Treatment Administration Deviation;
- Non-Permitted Medication;
- Assessment Performed Outside the Allowed Time Window;
- Visit Performed Outside the Allowed Time Window;
- Study Procedure Deviation;

Major and minor protocol deviations will be summarised using the Safety Set.

The number of subjects included in the Safety and PK Sets will be summarised.

All deviations, including significant GCP deviation, will be listed.

8.2 Demographic and Baseline Characteristics

8.2.1 Demographic Characteristics

Demographic characteristics will be summarised. These will include age (years) and race.

8.2.2 Physical Characteristics

Height (cm), weight (kg) and body mass index (BMI, kg/m²) will be summarized.

Note:

- BMI (kg/m²) will be calculated as: weight at the visit (kg) / height (m)² at Visit 1.

8.2.3 Alcohol Breath Test

Results of alcohol breath test will only be listed.

8.2.4 Spirometry at Screening

Spirometry results at Screening will only be listed.

8.3 Medical History and Concomitant Diseases

Medical/surgical history and concomitant diseases will be summarised by MedDRA system organ class (SOC) and preferred term (PT) using Safety Set.

Notes:

- medical/surgical history is defined as conditions in the medical/surgical history and concomitant diseases eCRF form which are not ongoing at Day 1;
- concomitant diseases are defined as conditions in the medical/surgical history and concomitant diseases eCRF form which are ongoing at Day 1.

8.4 Medications

Previous medications and concomitant medications will be summarised for the Safety Set through frequency distributions and percentages by Anatomical Main Group (1st level of the anatomical therapeutic chemical (ATC) classification), Therapeutic Subgroup (2nd level of the ATC classification), Chemical Subgroup (4th level of the ATC classification) and preferred name. Subjects with at least one prior/concomitant medications will also be summarized. Post-study medications will only be presented in a listing.

The medications will be classified according to the following rules:

- previous medication: medication start date < date of first study drug inhalation and stop medication date \leq date of first study drug inhalation;
- concomitant medication: date of first study drug inhalation \leq medication end date;
- post-study medication: medication start date \geq date of discharge.

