### 7.1.3 Follow-up

A follow-up call will be performed from 7 to 10 days after the discharge to perform the following:

- CONCOMITANT MEDICATIONS CHECK: concomitant medications taken to treat AEs by the subjects since the discharge will be checked and recorded in eCRF.
- ADVERSE EVENTS RECORDING: the status of unresolved AEs/SAEs at the discharge will be checked and any new AEs/SAEs occurred after the discharge will be recorded in the eCRF.

This safety follow-up call shall also be performed in case of premature discontinuation (7-10 days from the last administration intake).

If needed, according to the investigator's opinion, a follow-up visit can be performed.

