8.5 Procedures

Previous procedures and concomitant procedures will be summarised for the Safety Set through frequency distributions and percentages by MedDRA SOC and PT.

The procedures will be classified according to the following rules:

- previous procedures: procedure start date < date of first study drug inhalation and end procedure date \leq date of first study drug inhalation;

- concomitant procedures: date of first study drug inhalation \leq procedure end date;
- post-study procedures: procedure start date \geq date of discharge.

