10.2 Adverse Events

An AE will be classified as pre-treatment AE if it starts after the informed consent signature and before the time of first inhalation of the study drug (date of informed consent < AE onset date and AE onset date-time < date-time of first study drug inhalation).

All adverse events starting on or after the time of first study drug inhalation will be classified as treatment emergent adverse event (TEAE) (date-time of first study drug inhalation \leq AE onset date-time \leq date of discharge).

An AE will be classified as a post-study AE if it starts after the date of discharge (AE onset date $>$ date of discharge).

An adverse drug reaction (ADR) is an AE judged as related to the study medication.

A serious ADR is a serious AE (SAE) judged as related to the study medication.

A severe AE is an AE with severe intensity.

An AE leading to discontinuation will be identified based on the information collected in study termination form (i.e. reason for discontinuation =Adverse event).

An AE leading to death is an AE with outcome equal to “Fatal”.

Pre-treatment AEs, TEAEs and post-study AEs will be presented separately. Pre-treatment AEs and post-study AEs will be presented in the listings only.

The number of TEAEs, drug-related TEAE, serious TEAE and TEAE leading to study discontinuation and the number and the percentage of subjects experiencing TEAEs, drug-related TEAEs, serious TEAEs and TEAEs leading to study discontinuation will be summarised.

The MedDRA SOC and PT will also be used for tabulation. The number and percentage of subjects with at least one AE and the number of AEs will be presented by SOC and PT for the above categories of AEs.

Derived variables presented in the listings:

The relative day of AE onset will be calculated as follows:

- for pre-treatment AEs:
 - AE onset date - date of first inhalation of study drug (if AE onset date is completely known);
 - missing (if AE onset date is incomplete or unknown).
- For TEAEs and post-Study AEs:
 - AE onset date – date-time of first inhalation of study drug +1 (if AE onset date is completely known);
 - missing (if AE onset date is incomplete or unknown).

The duration of an AE (hours) will be calculated as follows:

- $(AE\ end\ date-time - AE\ onset\ date-time) / 3600$ (when both date-time are completely known)

The duration of an AE (days) will be calculated as follows:

If duration in hours ≥ 24 hours:

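### SAP 8.4 and 8.5 define concomitant by end date alone, so the previous, concomitant and post-study classes overlap

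*SAP*

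**What the plan says.** SAP 8.4 sorts medications into three classes by date. A drug is previous if it began before the day of first inhalation and was stopped no later than that day. The second class looks only at when the drug ended: "concomitant medication: date of first study drug inhalation \leq medication end date". The third class looks only at when it began, and counts the discharge day itself: "post-study medication: medication start date \geq date of discharge".

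Previous and concomitant medications are tabulated for the Safety Set. For the third class the section says: "Post-study medications will only be presented in a listing".

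SAP 8.5 applies the same three rules to procedures, for example "concomitant procedures: date of first study drug inhalation \leq procedure end date". It tabulates previous and concomitant procedures, but has no listing-only sentence for the post-study class.

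The only order of precedence among the classes is in SAP 7.3.1. It is concomitant, then post-study, then prior, and it applies "In case of missing or incomplete dates not directly allowing allocation to any category of medications".

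For adverse events, SAP 10.2 uses a different boundary: "An AE will be classified as a post-study AE if it starts after the date of discharge". An event with onset on the discharge date is therefore treatment-emergent.

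Post-discharge records will be collected. At the follow-up call, Protocol 7.1.3 says "concomitant medications taken to treat AEs by the subjects since the discharge will be checked and recorded in eCRF".

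**The concern.** The classes are evidently meant to be alternatives. SAP 7.3.1 assigns a doubtful record to one class by an order of preference, and SAP 8.4 sends the post-study class to a different output. The definitions do not deliver that. The concomitant rule tests only whether the drug ended on or after the first inhalation date, which every drug begun after discharge must do. The previous and concomitant rules both accept an end date equal to Day 1.

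A reader will use the concomitant table to see which other drugs were taken around dosing and sampling. Protocol 1.2 gives the absence of concomitant medication as a reason for studying metabolism in healthy subjects. A table that also holds drugs begun only after the last sample answers that question less cleanly. SAP 13.4 calls for independent double programming, and two programmers could resolve the overlap differently with nothing in the SAP to decide between them.

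**Working it through.** The plan states no figure here, so the check is of the rules themselves.

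**Inputs.** D = date of first inhalation = Day 1. X = date of discharge = Day 11 (Protocol 3, SAP 2). S and E are a record's start and end dates, with S ≤ E. All rules compare dates, not times.

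**Rules as written (SAP 8.4, repeated in 8.5).** Previous: S < D and E ≤ D. Concomitant: E ≥ D. Post-study: S ≥ X.

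**Overlaps.**

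1. Post-study and concomitant: if S ≥ X, then E ≥ S ≥ X > D, so E ≥ D always holds. Every post-study record with an end date also meets the concomitant rule.
2. Previous and concomitant: E ≤ D and E ≥ D together give E = D, with S < D. Every record begun before Day 1 and ended on Day 1 meets both.
3. Previous and post-study: S < D and S ≥ X cannot both hold.

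**Example records.**

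| Start | End | As written | With the fix below |
|---|---|---|---|
| Day -5 | Day -1 | previous | previous |
| Day -5 | Day 1 | previous and concomitant | concomitant |
| Day 3 | Day 5 | concomitant | concomitant |
| Day 11 | Day 12 | concomitant and post-study | concomitant |
| Day 14 | Day 15 | concomitant and post-study | post-study |

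**All start/end pairs from Day -14 to Day 21, with no Day 0.** There are 14 + 21 = 35 days, hence 35 × 36 / 2 = 630 pairs.

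- Concomitant and post-study (start on Day 11 to 21): 11 × 12 / 2 = 66
- Previous and concomitant (start before Day 1, end on Day 1): 14
- Previous only: 14 × 15 / 2 = 105
- Concomitant only: 630 − 66 − 14 − 105 = 445

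So 66 + 14 = 80 pairs fall in two classes and 550 in one. With the fix, previous has 105, post-study (start on Day 12 to 21) has 10 × 11 / 2 = 55, and concomitant has 630 − 105 − 55 = 470. None falls in two classes. The grid tests the logic; it does not predict how often such records occur.

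**Does SAP 7.3.1 help?** Not for complete dates, which it does not cover. If it were borrowed for them, concomitant comes first, and the post-study class would lose every record that has an end date. A post-discharge drug with no end date cannot be tested against the concomitant rule directly; if 7.3.1 is applied, it also goes to concomitant first.

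**Boundary with adverse events.** An event with onset on Day 11 is treatment-emergent under SAP 10.2. A drug started that day to treat it meets the post-study rule as well as the concomitant rule.

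**Size.** With 8 subjects in the Safety Set, one subject is 1/8 = 12.5%.

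**The case against.** The strongest reply is that the listing-only sentence sits in the same section as the definitions. Read as an output rule, it removes every post-study medication from the tables. A reader might infer that all post-discharge drugs with an end date will enter the wrong table. The documents do not support that: it happens only if the programmer gives the concomitant definition priority over that sentence. What stands is that the SAP does not say which prevails. The protocol also blurs the line, because its follow-up section calls drugs taken since discharge concomitant, and Protocol 5.2 extends the medication restrictions through follow-up.

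A reader might also infer that a drug stopped on Day 1 before dosing is wrongly called concomitant, and that times should be compared. That does not follow. Such a drug may still be on board during sampling, the rules use dates only, and the documents do not show whether the eCRF records medication times. The defect there is only that the drug appears in two tables. It does not touch the listing-only sentence.

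It is also fair to say that the harm is small. SAP 7.10 lists all eCRF data, SAP 8.1.3 makes non-permitted medication its own deviation category, and follow-up collection is directed at drugs taken to treat adverse events, so few records are likely.

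**Conclusion.** The point holds as a wording defect. As written, the classes overlap at two places: post-study with concomitant for every record with an end date, and previous with concomitant for records begun earlier and ended on Day 1. The first conflicts with the listing-only sentence for medications; for procedures it is a plain overlap. The discharge-day boundary also differs from the one used for adverse events.

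The effect is confined to the descriptive medication and procedure tables. In a Safety Set of 8, one misclassified subject changes a row by at most 12.5 percentage points, and by 0 if that subject already counts in the row. It would be wrong to read 12.5 points as the shift for every misclassified subject. The figure assumes a denominator of 8; Protocol 4.4 allows additional enrolment, which would make it smaller. The number of affected records is unknown. A reader might infer harm to the clearance, metabolism or safety results, but no PK or adverse event analysis uses these rules.

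**What to change.** In SAP 8.4, and likewise in 8.5, replace the three rules with these, using dates only:

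- previous: end date before the date of first inhalation;
- concomitant: end date on or after the date of first inhalation, or ongoing, and start date on or before the date of discharge;
- post-study: start date after the date of discharge.

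A drug stopped on Day 1 is then concomitant only, and the discharge-day boundary matches SAP 10.2. SAP 7.3.1 can stay as it is for incomplete dates. The cost is a few words in two sections and a few lines of derivation code. The small downside is that a drug started on Day 11 after the last sample counts as concomitant.
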